10.5.2 Time to FLU-PRO Domain Response

Definitions:

FLU-PRO Domain Response For each FLU-PRO domain (n=6), each item/symptom scored ≤ the maximum response value specified by the Symptom Response definition and maintained for at least two consecutive daily diary periods without symptom relief medication during or between those daily diary periods

Time of FLU-PRO Domain Response The start of the first daily diary period in which FLU-PRO Domain Response is achieved and is maintained for at least two daily diary periods without any symptom relief medication during or between those two daily diary periods.

Time to FLU-PRO Domain Response Time (hours) from the first dose of study medication to the Time of FLU-PRO Domain Response.

Variables Used for the Analysis

The analysis will require the following variables:

Variable	Source	Format/Notes
Date and time of first medication intake	CRF	
Date and time of completion for each symptom assessment record	Subject diary	
Symptom score assessment for each symptom for each diary record	Subject diary	The ordinal symptom severity, intensity or frequency score assessment for each of the 32 symptoms will be coded to numerical values 0-4. In the event that the diary was not completed at a specified time point (e.g., Day 2), the missing data will not be imputed.
Date and time of symptom relief medication intake	Sponsor-provided listing	The list of symptom relief medications will be selected from the listing of all concomitant medications prior to unblinding. Subjects will report the reason for taking each symptom relief medication, and this data will be used to assign concomitant medications to relevant domains captured in the FLU-PRO questionnaire.

Analysis

The efficacy parameter, Time to FLU-PRO Domain Response, will be derived as follows:

Event: Time of FLU-PRO Domain Response – time of the first dose

Censored: Time of last symptom assessment – time of the first dose

If FLU-PRO Domain Response is achieved at the time of the first symptom assessment diary record, the subject will be excluded from the analysis.

If the FLU-PRO Domain Response is not achieved prior to a subject’s last available diary assessment, but the criteria are met at the last available diary assessment with no evidence of symptom relief medication intake during that diary period, Time of FLU-PRO Domain Response will be considered to have occurred at the start of the last daily diary period.

Time to FLU-PRO Domain Response for the NTZ treatment group will be compared to that of the placebo treatment group using a Gehan-Wilcoxon test stratified for (1) time from onset of illness to time of first dose of study medication (0-24, >24-≤36, or >36 hours from onset), and (2) vaccination status (Y/N). The comparison will be graphically depicted using Kaplan-Meier curves.

Analysis Population(s):	Confirmed Influenza
Derived Variables:	Event: Time of FLU-PRO Domain Response – time of the first dose Censored: Time of last symptom assessment – time of the first dose

10.5.3 Time to Resolution of Acute Febrile Illness

Definitions:

Resolution of Acute Febrile Illness

Symptom scores for each of “body aches or pains”, “chills or shivering”, “felt cold”, “felt hot” and “sweating” are 0 or 1 and remain so for two consecutive daily diary periods with no record of oral temperature $\geq 100.4^{\circ}\text{F}$ ($<38^{\circ}\text{C}$) or symptom relief medication use for these symptoms during or between those two daily diary periods.

Time of Resolution of Acute Febrile Illness

The start of the first daily diary period in which Resolution of Acute Febrile Illness is achieved and is maintained for at least two daily diary periods without any symptom relief medication during or between those two daily diary periods.

Time to Resolution of Acute Febrile Illness

Time (hours) from the first dose of study medication to the Time of Resolution of Acute Febrile Illness.

Variables Used for the Analysis

The analysis will require the following variables:

Variable	Source	Format/Notes
Date and time of first medication intake	CRF	
Date and time of completion for each symptom assessment and temperature assessment record	Subject diary	
Oral temperature assessment for each temperature assessment record	Subject diary	Oral temperature will be recorded twice daily during the treatment period. This data is recorded contemporaneously with measurement in contrast to symptom diary data, which is intended to characterize maximum symptom intensity or frequency over a 24-hour recall period.
Symptom score assessment for each symptom for each diary record	Subject diary	The ordinal symptom severity, intensity or frequency score assessment for each of the five relevant symptoms will be coded to numerical values 0-4. In the event that the diary was not completed at a specified time point (e.g., Day 2), the missing data will not be imputed.
Date and time of symptom relief medication intake	Sponsor-provided listing	The list of symptom relief medications will be selected from the listing of all concomitant medications diaries prior to unblinding. Subjects will report the reason for taking each symptom relief medication, and this data will be used to assign concomitant medications to relevant symptoms captured in the FLU-PRO questionnaire.

Analysis

The efficacy parameter, Time to Resolution of Acute Febrile Illness, will be derived as follows:

Event: Time of Resolution of Acute Febrile Illness – time of the first dose

Censored: Time of last symptom assessment – time of the first dose

If there is a temperature assessment between diary assessments that is not <100.4°F (<38°C), the earliest a subject may achieve Resolution of Acute Febrile Illness is the start of the next daily diary period.

If the Resolution of Acute Febrile Illness is not achieved prior to a subject’s last available diary assessment, but the criteria are met at the last available diary assessment with no evidence of symptom relief medication intake during that diary period, Time of Resolution of Acute Febrile Illness will be considered to have occurred at the start of the last daily diary period.

Time to Resolution of Acute Febrile Illness for the NTZ treatment group will be compared to that of the placebo treatment group using a Gehan-Wilcoxon test stratified for (1) time from onset of

illness to time of first dose of study medication (0-24, >24-≤36, or >36 hours from onset), and (2) vaccination status (Y/N). The comparison will be graphically depicted using Kaplan-Meier curves.

Analysis Population(s):	Confirmed Influenza
Derived Variables:	Event: Time of Resolution of Acute Febrile Illness – time of the first dose Censored: Time of last symptom assessment – time of the first dose

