5.10 Electronic Subject Diary

Electronic subject diaries will be completed twice daily through day 21. The electronic diaries will capture the following information:

- 1) Medication intake (twice daily at time of medication intake).
- 2) Oral temperature (twice daily at time of medication intake). Use standard electronic oral thermometer provided by Sponsor. Oral temperature should, preferably, be recorded prior to acetaminophen dosing or greater than 4 hours after acetaminophen dose.
- 3) Use of other medications taken (including acetaminophen) by the subject not previously captured in the subject's medication history. Document in detail including dose in milligrams or other applicable units, time of ingestion, and the reason for use of the medication (at time of medication intake).
- 4) FLU-PRO Questionnaire (once daily between 7 pm and 11 pm) to characterize symptoms of influenza.
- 5) Activity assessment using an 11-point visual analog scale (0= unable to perform normal activity, 10= fully able to perform normal activity) (once daily between 7 pm and 11 pm).
- 6) Adverse experiences (once daily between 7 pm and 11 pm).

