Time of FLU-PRO Domain Response:

For each domain, the start of the first daily diary period in which the FLU-PRO Domain Response is achieved and is maintained for at least 2 daily diary periods without symptom relief medication during those 2 daily diary periods

Time to FLU-PRO Domain Response:

Time (hours) from first dose to FLU-PRO Domain Response for each domain

Resolution of Acute Febrile Illness:

Oral temperature is recorded by the patient as $<100.4^{\circ}\text{F}$ ($<38^{\circ}\text{C}$) and symptom scores for each of “body aches or pains”, “chills or shivering”, “felt cold”, “felt hot” and “sweating” are 0 or 1 and remain so throughout 2 daily diary periods without symptom relief medication during those 2 daily diary periods

Time to Resolution of Acute Febrile Illness:

Time (hours) from first dose to resolution of acute febrile illness.

Return to Usual Health:

“Yes” response to the daily FLU-PRO global assessment question, “Have you returned to your usual health today?” maintained for at least 2 daily diary periods without symptom relief medication during those 2 daily diary periods

Time of Return to Usual Health:

The time of the first daily diary entry in which Usual Health is achieved and is maintained for at least 2 daily diary periods without symptom relief medication during those 2 daily diary periods

Time to Return to Usual Health:

Time (hours) from first dose to Time of Return to Usual Health

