9.6 Disallowed Medication

The following medications will not be allowed during the study: any antiviral medication for flu or any prescription or non-prescription medications classified as (i) expectorants and cough preparations, (ii) analgesics and antipyretics or (iii) antihistamines (American Hospital Formulary Service (AHFS) classification). As an exception to this rule, subjects will be allowed to use acetaminophen as necessary for fever if oral temperature is $\geq 100.4^{\circ}\text{F}$ (38°C).

Medications for pre-existing conditions that are not excluded (see exclusion criteria) should be continued as prescribed. The use of such medication will be recorded in the EDC system.

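### SAP 10.5.3 lets acute febrile illness resolve without a temperature reading, unlike Protocol 8.3, and gives two conflicting medication rules for this exploratory endpoint

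*SAP*

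**What the plan says.** **Protocol 8.3.** Resolution has three parts. "Oral temperature is recorded by the patient as" below 100.4°F (38°C); the scores for aches, chills, feeling cold, feeling hot and sweating are 0 or 1 over two daily diary periods; and no symptom relief medication is used in those periods, whatever the reason.

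**SAP 10.5.3, definition of resolution.** The same five scores "are 0 or 1 and remain so for two consecutive daily diary periods with no record of oral temperature" at or above 100.4°F, and there must be no "symptom relief medication use for these symptoms during or between those two daily diary periods". The Celsius value in brackets carries a less-than sign.

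**SAP 10.5.3, definition of the time of resolution.** The event is dated to the start of the first daily period in which resolution "is achieved and is maintained for at least two daily diary periods without any symptom relief medication during or between those two daily diary periods".

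**SAP 10.5.3, analysis text.** A reading between diaries that is not below 100.4°F (38°C) moves the earliest possible resolution to the next daily period. This acts only if a reading exists. The rule for the last available diary looks for symptom relief medication without limiting it by reason. The section gives no rule for a missing temperature.

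**Collection of temperature.** The SAP says "Oral temperature will be recorded twice daily during the treatment period". Protocol 5.10 lists "Oral temperature (twice daily at time of medication intake" within a diary that is kept through Day 21.

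**Neighbouring endpoints.** The definitions in SAP 10.5.1 and 10.5.2 bar symptom relief medication without limit by reason, as Protocol 8.3 does. Notes in their variable tables nevertheless allocate medication by reported reason; in 10.5.2, "this data will be used to assign concomitant medications to relevant domains captured in the FLU-PRO questionnaire".

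**The concern.** An endpoint named resolution of febrile illness should not be met because nobody took a temperature, nor should its event time depend on which of two adjacent sentences the programmer follows. The SAP changes a criterion that needs a reading into one that needs only the absence of a high reading, and it does so where it also expects readings to stop after dosing. On medication, the section limits the bar by reason in one place and not in the next.

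The endpoint is exploratory, but it is likely to be read closely. Protocol 1.2.5 and 1.2.6 report nominal benefit on a composite of fever, feverishness and myalgia in two earlier trials that missed their primary endpoints (nominal p=0.004 in RM08-3003). Whatever this trial shows on febrile illness will be set beside those results.

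**Working it through.** The documents attach no sample size, power or alpha calculation to this endpoint, so the check compares the rules.

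**Step 1. Threshold.** (100.4 − 32) × 5/9 = 68.4 × 5/9 = 38.0°C. The pair 100.4°F and 38°C is right, so the less-than sign before 38°C in the SAP definition is reversed.

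**Step 2. One window under each rule.** Take two consecutive daily periods with all five scores at 0 or 1, and read the SAP threshold in Fahrenheit.

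| Temperature in window | Medication | Protocol 8.3 | SAP, resolution | SAP, time of resolution |
|---|---|---|---|---|
| All below 100.4°F | None | Resolved | Resolved | Resolved |
| Some missing, rest below | None | Depends on whether every reading is needed | Resolved | Resolved |
| None measured | None | Not resolved | Resolved | Resolved |
| All below 100.4°F | For one of the five symptoms | Not resolved | Not resolved | Not resolved |
| All below 100.4°F | For another reason | Not resolved | Resolved | Not resolved |
| None measured | For another reason | Not resolved | Resolved | Not resolved |
| Any at or above 100.4°F | Any state | Not resolved | Not resolved | Not resolved |

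The third row is the temperature departure: both SAP sentences differ from the protocol. The fifth and sixth rows are the medication contradiction: the two SAP sentences differ from each other, and the second agrees with the protocol.

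**Step 3. What the medication contradiction does to one event time.** Suppose, for illustration, that scores are at 0 or 1 and all readings are below 100.4°F from Day 3 on, and that medication is taken for headache on Days 3 and 4 only. By the resolution sentence alone, the Day 3 and 4 window qualifies and the event falls at the start of the Day 3 period. By the time-of-resolution sentence, the first clean window is Days 5 and 6. The gap is 2 × 24 = 48 hours between the two SAP sentences. Between the time-of-resolution sentence and Protocol 8.3 it is 0 hours.

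**Step 4. Where the temperature test is empty.** If collection follows the SAP, with a 5-day treatment period and a diary through Day 21, there are 21 − 5 = 16 days without a scheduled reading, and 16/21 = 76%. If Protocol 5.10 is read as collection for the whole diary, the figure is 0 of 21. The documents do not settle which applies.

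**Step 5. Literal Celsius sign.** Taken at face value and without medication, it would leave a window with all readings below 38°C unresolved and make one with all readings at or above 38°C resolved. That is absurd. The Fahrenheit value beside it, the analysis text of the same section and Protocol 8.3 all contradict it.

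**The case against.** **The endpoint is exploratory.** Protocol section 3 and SAP 10.5 place it outside the testing hierarchy. This stands and limits the weight of the point.

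**The SAP wording is workable and partly deliberate.** The revision history lists a clarification of how medication affects this endpoint, and Protocol 8.4 leaves detail to the SAP. If temperature stops with dosing, no window wholly after treatment could satisfy a literal need for a reading, so the protocol text cannot simply be restored. This also stands, and it shapes the fix. It does not explain the missing rule for the treatment period, and the clarification left the time-of-resolution sentence unaligned.

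**The temperature gap may matter little.** A reader might take the 76% to mean that most resolutions rest on unmeasured temperature. It counts calendar days, not subjects or events. The all-symptom median times in RM08-3001 and RM08-3003 ran from 95.5 to 116.7 hours, inside 5 × 24 = 120 hours, although on another instrument. A window without readings still needs all five scores at 0 or 1.

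**Acetaminophen for fever.** A reader might infer that permitted antipyretic use never blocks resolution. Protocol 9.6 says "subjects will be allowed to use acetaminophen as necessary for fever if oral temperature is" at least 100.4°F (38°C). That reading, if recorded in the diary, itself blocks the window, and fever plausibly maps to feeling hot, one of the five items. Acetaminophen for headache is disallowed, but under Protocol 9.5 it does not end participation, so such subjects can still contribute events.

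**A 48-hour error against the protocol.** A reader might also infer this from the medication wording. It does not follow: the sentence that dates the event gives the same time as the protocol. The defect there is that two sentences conflict.

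**Conclusion.** The point holds as a departure from the protocol and an internal contradiction in the definition of one exploratory endpoint. On temperature, a window without readings resolves under both SAP sentences and not under Protocol 8.3. After scheduled collection ends, the SAP test is met by default unless a high reading happens to be recorded. On medication, the two SAP sentences can date the same subject differently, by 48 hours in the illustration. The Celsius sign is a typographical error and does not by itself cause false resolution.

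The conclusion rests on reading Protocol 8.3 as needing at least one actual reading, and on the SAP's statement of when temperature is collected. The documents give no rate of missing temperatures or of medication for other reasons. Neither the number of affected subjects nor the direction of any bias can therefore be determined, and an inference that either arm is favoured has no support. The primary result, hierarchy and sample size are unaffected.

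**What to change.** In SAP 10.5.3, before database lock:

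- **Temperature.** Reconcile the collection window with Protocol 5.10 and state it. While temperature is scheduled, let a daily period qualify only with at least one recorded reading and all readings below 100.4°F (38°C). After scheduled collection ends, use the symptom criteria with no recorded reading at or above 100.4°F, counting any later diary reading and the Day 7 and Day 22 clinic readings. Do not bar a subject permanently because the last treatment-period reading was high; that would censor someone who has since recovered. Report by arm how many events rest on windows without a reading.
- **Medication.** Use one analysis rule, no symptom relief medication for any reason, in both definitions, to match Protocol 8.3. Keep the reason-based rule as a supportive run only. In 10.5.1 and 10.5.2 the definitions already match the protocol; only the reason-allocation notes in their variable tables need to be brought into line.
- **Sign.** Print the Celsius limit as at or above 38°C.

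The cost is SAP wording and programming on data already planned, with the clinic temperatures added as a source. Some resolution times will become later. SAP version 1.2 carries no final date in the revision history, and SAP section 6 allows amendment until lock.

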10. EFFICACY

10.1 General

Unless otherwise specified, all statistical tests will use two-sided tests at the $\alpha=0.05$ level.

The following definitions will apply to multiple efficacy analyses:

- Daily Diary Period Each daily diary period will begin 24 hours prior to the time of diary assessment and end at the time of diary assessment.
- Symptom Relief Medication Any medication taken for a symptom of influenza as indicated by the subject during the study period.

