10.2.2 Analysis of the Primary Efficacy Parameter

The primary efficacy parameter, time to Symptom Response, will be derived as follows:

Event: Time of Symptom Response – time of the first dose
 Censored: Time of last symptom assessment – time of the first dose

If Symptom Response is achieved at the time of the first symptom assessment diary record, the subject will be excluded from the analysis.

If Symptom Response is not achieved prior to a subject’s last available diary assessment, but the criteria are met at the last available diary assessment with no evidence of symptom relief medication intake during that diary period, time of Symptom Response will be considered to have occurred at the start of the last daily diary period.

Time to Symptom Response for the NTZ treatment group will be compared to that of the placebo treatment group using a Gehan-Wilcoxon test stratified for (1) time from onset of illness to time of first dose of study medication (0-24, >24-≤36, or >36 hours from onset), and (2) vaccination status (Y/N). The comparison will be graphically depicted using Kaplan-Meier curves.

Analysis Population(s):	Confirmed Influenza
Derived Variables:	Event: Time of symptom response – time of the first dose Censored: Time of last symptom assessment – time of the first dose

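### SAP 10.5.3 has no rule for subjects who already meet the febrile-illness resolution criteria at the pre-dose baseline record, so their event times fall about 24 hours or more before first dose

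*SAP*

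**What the plan says.** SAP 10.5.3 counts acute febrile illness as resolved when five FLU-PRO items (aches, chills, feeling cold, feeling hot, sweating) "are 0 or 1 and remain so for two consecutive daily diary periods", with no temperature of 100.4°F or above and no relief medication for these symptoms during or between those periods. The time of resolution is "The start of the first daily diary period in which Resolution of Acute Febrile Illness is achieved", and the analysis variable is "Event: Time of Resolution of Acute Febrile Illness – time of the first dose". SAP 10.1 fixes the period: "Each daily diary period will begin 24 hours prior to the time of diary assessment and end at the time of diary assessment".

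Two further rules in 10.5.3 adjust the event time. One delays resolution after a reading that is not below 100.4°F, so that "the earliest a subject may achieve Resolution of Acute Febrile Illness is the start of the next daily diary period". The other deals with subjects who first meet the criteria at their last record. Neither addresses a subject who meets them at the first record, and no lower limit is set at first dose.

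The primary analysis has such a rule in SAP 10.2.2: "If Symptom Response is achieved at the time of the first symptom assessment diary record, the subject will be excluded from the analysis". Equivalent sentences stand in 10.4.1, 10.4.3, 10.5.1, 10.5.2 and 10.5.4; for domain response it reads "If FLU-PRO Domain Response is achieved at the time of the first symptom assessment diary record, the subject will be excluded from the analysis". Of the seven diary time-to-event analyses, only 10.5.3 lacks one.

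**The concern.** An event dated to the start of a period that ended before the first dose cannot be a time from first dose to anything. It records the resolution of an illness that, by the endpoint's own criteria, was not present at baseline.

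The SAP does not say what happens to such times. If they are kept, they are the earliest events in the analysis, where the Gehan-Wilcoxon weight (the number at risk) is largest. If software discards negative times, subjects leave the analysis without a prespecified rule. A choice between the two made after unblinding would be open to challenge.

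**Working it through.** The plan gives no figure for this point, so the check applies its definitions directly.

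**Inputs**
- A diary period runs from 24 h before the assessment to the assessment (SAP 10.1).
- Event time T = start of the first qualifying period minus time of first dose (SAP 10.5.3).
- The supervised baseline diary is step 6 of the baseline visit and the first dose is step 8 (Protocol 5.2).
- Regular FLU-PRO entries are made once daily between 19:00 and 23:00 (Protocol 5.10).
- Assumed, not in the documents: a gap g of 0 to 2 h between baseline diary and first dose, and a first dose between 08:00 and 18:00.

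**Step 1. Can such subjects be enrolled?** Yes; the two sets of criteria differ:

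| | Entry (Protocol 4.1) | Resolution (SAP 10.5.3) |
|---|---|---|
| Temperature | 99.4°F or above | none at or above 100.4°F |
| Symptoms | one respiratory and one constitutional; fatigue or headache suffices | five items at 0 or 1; neither fatigue nor headache is among them |

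A subject with cough, fatigue and 99.6°F is eligible and may score 0 or 1 on all five items.

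**Step 2. First qualifying record is the baseline diary.**
T = (-g - 24) - 0 = -(24 + g) h.
- g = 0: T = -24 h
- g = 0.5: T = -24.5 h
- g = 1: T = -25 h
- g = 2: T = -26 h

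**Step 3. First qualifying record is the Day 1 evening diary** (clock time e, dose at clock time d).
T = (e - d) - 24.
- e = 23, d = 8: T = -9 h
- e = 19, d = 18: T = -23 h

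This is still negative throughout. A first-record exclusion would not catch it if the baseline diary is the first record.

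**Step 4. First qualifying record is the Day 2 evening diary.**
T = (e + 24 - d) - 24 = e - d, from 19 - 18 = +1 h to 23 - 8 = +15 h. From here on, event times are positive.

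**Step 5. Consistency within the SAP.** A subject scoring 0 on all five items from the first record, without relief medication, is excluded from all five corresponding individual-symptom analyses in 10.5.1, because 0 satisfies any maximum response value. Provided no temperature reaches 100.4°F, 10.5.3 counts the same subject as a resolution before treatment.

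**Step 6. How many?** The documents do not say. For an assumed share of 600 subjects meeting the criteria from the baseline record:

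| Assumed share | Event times of -24 h or earlier | Left if excluded |
|---|---|---|
| 1% | 600 × 0.01 = 6 | 594 |
| 5% | 600 × 0.05 = 30 | 570 |
| 10% | 600 × 0.10 = 60 | 540 |
| 20% | 600 × 0.20 = 120 | 480 |

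**The case against.** The strongest reply is that the consequence is small. The endpoint is exploratory and outside the testing hierarchy in SAP 10.4. Under 1:1 randomisation, subjects with few febrile symptoms at baseline should be balanced between arms. If software drops negative times, the result approximates the exclusion used elsewhere. All of this stands, and it limits the point to a minor correction. It does not supply the missing rule.

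Two technical replies also stand and shape the remedy.
- Resolution needs two periods, and the second qualifying record falls after first dose. Whether a subject counts as resolved from baseline therefore depends partly on the post-dose course, so these events are not wholly free of treatment information. Copying the exclusion sentence from the other sections could remove a low-symptom subject who stays low while keeping one who worsens.
- The missing rule is not the only source of negative times. Symptom response, modified symptom response, individual symptom response and domain response are also dated to the start of a period, so Step 3 can arise there despite their first-record rules.

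A reader might infer that every subject without fever at entry is affected. The text does not support that: all five items, the temperature and the relief-medication condition must hold across two consecutive periods. A reader might also infer that this same endpoint was nominally positive in RM08-3002 and RM08-3003. The composite in those trials was fever, feverishness and myalgia, taken from a different symptom diary (Protocol 1.2.5 and 1.2.6), so those results do not carry over to the present definition.

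**Conclusion.** The gap is real. As written, 10.5.3 gives an event time of -(24 + g) h to any subject who meets the criteria at the pre-dose baseline record and through the next diary period. Nothing else in the SAP or protocol repairs this, and no reason is given for treating this endpoint differently from the other six.

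The -24 h result rests on the baseline diary counting as the first record and preceding the dose, as the order of steps in Protocol 5.2 indicates. If the Day 1 evening diary is the first qualifying record instead, the times are -9 to -23 h under the assumed dosing hours, which are still invalid. The 6 to 120 subjects rest entirely on an assumed 1% to 20% share.

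The expected effect is dilution and an undefined analysis set. The documents give no ground for inferring a bias towards either arm or an inflated type I error, and the gap leaves the primary result and the hierarchy unaffected.

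**What to change.** Before unblinding, make two changes to the SAP.

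1. In 10.5.3, restrict the analysis to subjects whose baseline record does not meet the resolution criteria. Judge this on the baseline symptom scores and temperature alone, and name the temperature source, so that exclusion does not depend on any post-dose record.
2. In 10.1, state that an event time dated to the start of a diary period that falls before first dose is set to 0. Apply this to every endpoint dated that way (10.2.2, 10.4.3, 10.5.1, 10.5.2 and 10.5.3), since a floor in 10.5.3 alone would create a new inconsistency.

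The cost is a few sentences and somewhat fewer subjects in an exploratory analysis. For a rank test the floor only ties the pre-dose times with one another; it does not move them past any positive time, and it prevents their silent loss in software.
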